- *What are the health economic impacts of using CFDP?*
 - The study will identify and compare healthcare resource utilisation, and associated costs, of both pathways using data collected from HES, NHS BSA, and local clinical records.

Secondary

- *What are the long-term impacts of treatment in terms of antibiotic use, pain experienced, anxiety, further treatment required by CFDP compared to treatment through a traditional pathway?*
 - Using a text message questionnaire, data will be collected from parents/guardians regarding antibiotic use, pain experienced and anxiety of the patient.
- *What are dental teams' beliefs and views on CFDPs/traditional pathways?*
 - Using a qualitative methodology dental team views will be recorded and analysed.
- *Are patients satisfied with their experience in using CFDPs and traditional services?*
 - Patient experience will be recorded using an adapted version of the NHS Friends and Family Test recorded through a text message questionnaire.
- *Looking only at the CFDPs - what proportion require an onward referral and what characteristics necessitate an onward referral?*
 - The project will assess the characteristics of patients who do and do not require onward referral.
- *Does the scheme work differently across different localities, for different patients?*
 - The project will determine similarities and differences in how CFDP sites operate for the patients they see and treat.

II. INVESTIGATORS

Key Contacts

The Principal Investigator for this study will be:

[name]
University of Manchester
Dental Health Unit
[name]

Other individuals involved in this study include:

[name] [contact]
(University of Manchester; Statistician)

[name] [contact]
(University of Cambridge; Realist evaluation)

[name] [contact]
(University of Manchester)

[name] [contact]
(University of Liverpool; Consultant Dental Public Health)

[name] [contact]
(University of Manchester; Health Economist)

[name]
(Lay co-applicant / PPI advisor)

III. APPROVAL OF THE PROTOCOL

The protocol has been reviewed and approved in writing by NHS ethics (IRAS ID: 323977 REC Reference: 23/EM/0093), and The University of Manchester as sponsor.

The Principal Investigator will ensure all relevant staff participating in the study have appropriate training prior to study commencement.

IV. DURATION OF STUDY

3 Years (see timeline).

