- Secondary care resource use: dental extractions under GA. Data collected from routine data: HES and CDS software
- Intervention resource use for CFDP pathway: additional costs paid to deliver the pathway (as outlined in the service level agreement) and additional costs in terms of setting up the pathways (providing training and resources/support for dentists. Data collected from CFDP providers and commissioners.

Unit costs will be attached to dental treatments via the dental treatment band and the associated Units of Dental Activity cost. Unit costs for prescribed antibiotics will be obtained from Prescriptive Cost Analysis data (21). Unit costs for secondary care resource use are sourced from the Healthcare Resource Group tariffs for tooth extractions(22).

Intervention costs will be attached data from CFDP providers and commissioners using salary costs from Unit Costs of Health and Social Care (23). The cost per patient for each pathway will be summarised and presented adjusted for inflation.

The health economics analysis will adopt a cost-consequences approach whereby the costs of each pathway will be presented separately but alongside relevant outcomes: 1) dental extractions under GA, 2) count of children who are successfully seen and treated in each pathway, 3) count of treatments performed (extractions, restorations), 4) mean wait time and 5) dental pain experienced by a child. Resource use and costs from the CFDP pathway will also be used in a budget impact analysis. Differences in outcomes will be generated from the quantitative analysis.

The analysis will take an NHS perspective with a 2 year time horizon. Longer term costs and outcomes will not be modelled due to the need for treatment being acute and focusing on child teeth. This approach will provide dental service commissioners with appropriate health economic data to inform future commissioning decisions related to CFDP.

VII. Monitoring of the study

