- Supplemental routinely collected pseudonymized dental data for all children who were eligible to be seen within a CFDP will be acquired from the dental referral management system and data collected by commissioners and sent to the University of Manchester to be stored in the research data storage. Additionally, identifiable data with assigned ID numbers for these same children will be provided by the dental referral management system to NHS England and NHS BSA following the approval of the Confidentiality Advisory Group (CAG). Pseudo anonymised data provided from NHS England, NHS BSA following linkage with the dental referral management system, will be sent to the University of Manchester Data Safe Haven.
- The Dental Referral Management System will assign unique ID numbers to the pseudonymized data. The RMS system will securely store the identification key, ensuring that only authorized personnel within the system can access it. It will be destroyed as soon as the pseudo anonymised data has been provided to UoM.
- Participants will be shared a copy of their consent via email or via post.
- Audio recordings will be transferred to UoM storage after interviews and deleted from the audio recording device.
- Audio recordings will be kept for as long as the hard copy consent would be.
- Consent will be kept separately to research data

Data will be securely stored securely at the University of Manchester. Where necessary this will be within system compliant for NHS data, all other data will be stored within Isilon storage which is normally used for research data. If NHS/clinical data need to be combined for analysis this will occur within the Data Safe Haven.

All data will be pseudo anonymised. The key will be stored on a separate system from clinical data provided by NHS. With participant consent identifiable information will be provided to third parties such as NHS BSA in order to link the data and for these parties to provide pseudo anonymised back to the study team as part of this research.

Two years after the completion of the study consent forms will be destroyed, the key detailing the connection between identifiable data and ID will be destroyed which will ensure all data is fully anonymised.

IX. Randomization

Not applicable. Prospective, comparative, population based study.

X. DATA ANALYSES

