Summary descriptive data will be reported by study arm and overall using tables of frequencies or means and standard deviations as appropriate to characterise the population and identify any imbalance between groups. The comparison of outcomes from the traditional specialist dental service route (control) compared to the intervention treatment under the alternative Child-Friendly Dental Practice will be assessed to determine if there are clinically meaningful and statistically significant differences in key outcomes. The primary outcome is receipt of GA for tooth extraction within two years of initial referral. Referral along both pathways may still result in the need for a GA for some children but a key metric will be to determine whether there

is a meaningful difference in the number of GAs per referral pathway. The primary outcome will be analysed using a mixed effects logistic regression model, accounting for the traditional specialist dental service route or alternative Child-Friendly Dental Practice, with random effects for centre. An adjusted logistic regression analysis additionally accounting for the age, deprivation, ethnicity, sex of the child along with the number of teeth requiring treatment at initial examination (through the CFDP or CDS) will also be undertaken. The analysis dataset will include all participants for whom there is follow-up data from the NHS BSA and the baseline covariates.

Analysis of secondary outcomes will be undertaken in a similar manner using covariate adjusted linear or logistic regression models as appropriate, we will include the modifying effect of deprivation

The health economics analysis will adopt a cost-consequences approach whereby the costs of each pathway will be presented separately but alongside relevant outcomes: 1) dental extractions under GA, 2) count of children who are successfully seen and treated in each pathway, 3) count of treatments performed (extractions, restorations), 4) mean wait time and 5) dental pain experienced by a child. Resource use and costs from the CFDP pathway will also be used in a budget impact analysis. Differences in outcomes will be generated from the quantitative analysis.

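### Comparing pathway costs is a primary objective, but the stated analysis only summarises each pathway's cost separately, adjusted for inflation, which leaves the comparison open to case-mix confounding

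*Protocol*

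**What the plan says.** The Research objectives section of the protocol puts two questions under its primary heading. The first is GA over two years. The second is "What are the health economic impacts of using CFDP", and its objective reads: "The study will identify and compare healthcare resource utilisation, and associated costs, of both pathways".

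The analysis is described under Cost effectiveness and again, in nearly the same words, in section X (Data analyses). It is a cost-consequences analysis from an NHS perspective over two years, in which "the costs of each pathway will be presented separately but alongside relevant outcomes". Cost effectiveness adds: "The cost per patient for each pathway will be summarised and presented adjusted for inflation". Both places say: "Differences in outcomes will be generated from the quantitative analysis". A budget impact analysis is also planned, drawing on CFDP resource use and costs.

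For GA, section X names a mixed logistic model with pathway and a random centre effect, and then "An adjusted logistic regression analysis additionally accounting for the age, deprivation, ethnicity, sex of the child along with the number of teeth requiring treatment". Secondary outcomes get "covariate adjusted linear or logistic regression models as appropriate". Cost is neither in the list of secondary outcomes nor among the five outcomes to be shown beside the costs.

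On allocation, section IX (Randomization) says: "Not applicable. Prospective, comparative, population based study".

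**The concern.** The objective says compare, but the stated method stops at a summary for each pathway. Followed as written, it produces two cost figures and no defined difference or interval. A reader who wants the answer to the second primary question would have to subtract one figure from the other.

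In a non-randomised cohort that subtraction mixes any effect of the pathway with differences between the children. The protocol treats such differences as possible: it plans tables to look for imbalance and adjusts GA for age, deprivation, ethnicity, sex and number of teeth needing treatment. GA extraction is also the only secondary-care item costed. A case-mix difference that the adjusted GA model would allow for could therefore remain in the cost figures printed beside it.

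Much rests on this comparison. The rationale cites a worry that the scheme could cost more overall than usual care. The risks and benefits text says the CFDPs will continue, expand or cease as a result of the project.

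**Working it through.** **1. The plan's own figures.** The protocol gives no cost mean, standard deviation, difference or precision, so there is no cost figure to reproduce. Its one design calculation is for GA: 25% v 15%, 90% power, two-sided 0.05.

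- Without continuity correction: n = [1.960 × √(2 × 0.20 × 0.80) + 1.282 × √(0.25 × 0.75 + 0.15 × 0.85)]² / 0.10² ≈ 334.2, so 335 per group.
- With continuity correction: (334.2/4) × [1 + √(1 + 4/(334.2 × 0.10))]² ≈ 353.9, so 354 per group and 708 in total, as stated.

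That figure is sound on its own terms and is unaffected by this point. It also shows that the study was sized on GA alone.

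**2. Objective and method side by side.**

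| Element | Stated for outcomes | Stated for cost |
|---|---|---|
| Objective | Compare pathways | Compare pathways |
| Between-pathway difference | Yes, from the quantitative analysis | None named |
| Case-mix covariates | Yes, in the adjusted GA model and the secondary-outcome models | None named |
| Centre | Random effect in the GA model | None named |
| Other adjustment | – | Inflation |

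No stated rule brings cost into the regression models. The budget impact analysis, as described, draws on CFDP costs and supplies no contrast with the traditional pathway.

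**3. Could case mix differ?** Both cohorts are limited to children triaged as suitable for a CFDP, which narrows the gap. Two features leave room for one. Recruiters at the Community Dental Service (CDS) may themselves identify eligible children. The CFDP group is also topped up with unconsented referral-system records, while the comparison group is consented (Screening, Selection and Recruitment; Sample size).

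**4. How large could it be?** The documents cannot say. Two illustrations follow, both on assumptions and both with no true pathway effect.

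*Total cost.* Let a share p of children be higher-severity, each costing r times a lower-severity child. Mean cost, in units of a lower-severity child, is 1 − p + pr. The gap is shown as a percentage of the costlier pathway's mean.

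- 50% v 40%, r = 1.5: (1.25 − 1.20)/1.25 = 4.0%.
- 50% v 30%, r = 2: (1.50 − 1.30)/1.50 = 13.3%.
- 60% v 30%, r = 3: (2.20 − 1.60)/2.20 = 27.3%.

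*GA component only.* Let C be the unit cost of a GA extraction, which the protocol does not give. The design contrast is worth (0.25 − 0.15)C = 0.10C per child. Assumed gaps of 2, 5 and 10 points in underlying GA risk would move unadjusted cost by 0.02C, 0.05C and 0.10C. The sign could go either way, so this could create an apparent saving or hide a real one.

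**The case against.** The strongest reply is that showing costs by pathway beside outcomes is what a cost-consequences analysis is, and that the regression for cost belongs in a statistical or health-economics analysis plan that is not shown. The protocol does fix the perspective, horizon, resource items and unit-cost sources, and nothing in it forbids a cost difference or an interval.

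Much of this stands. Separate display is not an error, and the choice of cost model can be left to a later plan. What remains is that the protocol is not silent on method. It says twice how costs will be presented, names one adjustment, and promises differences for outcomes only. That method falls short of its own primary objective.

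A reader might also infer more than the text supports:

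- **That crude mean costs are planned.** The protocol says only that cost per patient will be summarised. The absence of case-mix adjustment is inferred from inflation being the only adjustment named.
- **That the comparison is confounded.** No cost or case-mix data are given, and both cohorts are restricted to CFDP-eligible children. Open to confounding is as far as the text goes.
- **That the two halves of the table necessarily stand on different bases.** The first-named GA model has only pathway and centre, and the protocol does not say which model feeds the economic table. Several of the listed outcomes are themselves counts or means by pathway.
- **That cost is a second confirmatory endpoint.** GA is the only primary outcome and the only basis for the sample size, and no test on cost is planned.

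**Conclusion.** The point holds as a mismatch between a primary objective to compare costs and a stated analysis that summarises them by pathway with inflation as the only named adjustment. In a non-randomised cohort the resulting comparison is open to case-mix confounding, and it may not match the basis of the covariate-adjusted outcome differences beside it.

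Its size and direction are unknown. The range of about 4% to 27% depends wholly on assumed severity shares and cost ratios. The 0.02C to 0.10C range depends on assumed gaps in GA risk and leaves out dental treatment, antibiotics and the cost of setting up and running the CFDP pathway. Neither is a prediction, and neither supports a claim that the study will report a false saving. GA extractions appear in the same table, so an apparent saving without a GA difference would be at least partly visible. The change is worth making before analysis. The GA design and sample size are not affected.

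**What to change.** Keep the cost-consequences table. Under Cost effectiveness and in section X, add that the second primary question will be answered by the difference in mean two-year NHS cost per child, CFDP minus traditional, with a 95% interval. State that:

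- it uses the same baseline covariates, analysis set and accounting for centre as the adjusted GA model;
- it is reported as an estimate, not a test;
- the unadjusted cost per patient for each pathway is shown alongside;
- the outcome differences placed beside it come from the covariate-adjusted models.

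The form of the cost model can be left to the analysis plan.

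The cost is a few lines of wording and one more regression on data already planned for collection. With about 20 centres (at least 10 per pathway) the interval will probably be wide, and adjustment covers only the covariates that are measured. Commissioners would still see how uncertain the cost difference is, which two separate averages would not show.

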Appendix A – Gantt Chart

APPENDIX B – Data collection

Data collected through CDS

ID	Contract Number	Provider Name	Locality	Month of Submission to Dental Comm Team	Practice patient code	Pt Age (in years)	Patient Postcode	URN	Referring Practice Name	Referring GDP Name	Referring Practice Postcode	Number of courses of Antibiotics whilst waiting?

Date of Referral	Appt made? (Yes / No)	Reason no appt (Please select from the drop down)	Number of appts attended	Number of appts WNB	Bitewings taken?	Date of Initial Appointment	Number of decayed teeth needing treatment *at CDS	Outcome (please select from drop down)

Treatment Provided								Notes	Who carried out treatment	Previously seen at CFDP or other services after referral	GM central emergency system (Out of hours) Y/N
Number of Filling(s)	Number of Extraction(s)	Number of Stainless Steel Crowns (SSCs)	Number of Temp Fillings	Fluoride Varnish Application (Y/N)	Silver Diamine Fluoride (SDF) (Y/N)	Oral Health Improvement Advice Given (Y/N)	Antibiotics (Yes / No)				

Data collected through CFDP

ID	Contract Number	Provider Name	Locality	Month of Submission to Dental Comm Team	Practice patient code	Pt Age (in years)	Patient Postcode	URN	Referring Practice Name	Referring GDP Name	Referring Practice Postcode

Number of courses of Antibiotics whilst waiting?	Date of Referral	Appt made? (Yes / No)	Reason no appt (Please select from the drop down)	Date of Initial Appointment	Number of appts attended	Number of appts WNB	Bitewings taken?	Number of decayed teeth needing treatment
			Cannot contact					

Treatment Provided								Outcome (please select from drop down)	Notes	Who carried out treatment	GM central emergency system (Out of hours) Y/N	Patie
Number of Filling(s)	Number of Extraction(s)	Number of Stainless Steel Crowns (SSCs)	Number of Temp Fillings	Fluoride Varnish Application (Y/N)	Silver Diamine Fluoride (SDF) (Y/N)	Oral Health Improvement Advice Given (Y/N)	Antibiotics (Yes / No)					

NHS BSA data headings

Link	Flagged (linked or not linked data set 0 = not linked, 1 = linked)
PANDA_ID	PANDA ID (include if linked)
PATIENT_ID	Patient ID (random number generated by NHS BSA for each patient)
Age of Pt at every CoT	age of Pt at every CoT (will need to use DOB and treatment date)
GENDER	Gender
PT_LSOA	Lower Super Output Area of patient's home address at time of treatment

IMD	UoM will supply this as a post-code lookup. IMD against NEPU 2019 scores an
IMD rank	
Patient_charge_due	Patient charge due (££) for ever CoT
Patient_charge_collected	Patient charge actually collected (i.e. if they did not complete the course of treatment - are there outstanding payments owed? = remittance)
TX_COMPLETE	Is the treatment complete or incomplete? NO=0, Y=1
TX_DAYS	Interval in days between date of acceptance and date of completion or last visit
YEAR_MONTH	Date of when the form was submitted
TREATMENT_DATE	date of treatment
TREATMENT_CHARGE_BAND	treatment charge band
CONTRACT_TYPE	Type of contract (we are requesting information on: GDS / GDS and / PDS - no ortho needed).
12_MONTH_LIST	ND looking into this = Number of unique patients seen in previous 12 months (contract level)
24_MONTH_LIST	ND looking into this - Number of unique patients seen in previous 24 months (contract level)
PRACTICE_LSOA	Lower super output area of dental practice address
PRACTICE_CCG	Clinical commissioning group of dental practice address
PRACTICE_CCG_POPULATION_PER_DENTIST	Population per dentist of practice Clinical Commissioning Group
CONTRACT_UDAs	Annual number of contracted UDAs
CONTRACT_UDA_VAL	UDA Value (price per UDA)
CONTRACT_RADS_PER_100	Radiographs rate per 100 FP17s for contract (unless this is available by performer?)
CONTRACT_REATTEND	Average Re-attendance interval (days) on contract. I.e. number of days between courses of treatment completion and start of new course of treatment
FORM_ID	Is this just each treatment line - if so keep in
FOUNDATION_DENTIST	foundation dentist
AGE_LAST_3103	Dentists age. Age at that CoT (Age at march of that year - preceding treatment)
PERFORMER_NUMBER	NHS BSA to TRANSFORM into another numeric value to allow us to still identify the same performers within the dataset but not linkable to any real-world information
PERFORMER_PROVIDER	Is the performer also a provider (i.e. contract holder)? N=0, Y=1
PERFORMER_DATE_REGISTERED	Date of performer entry to General Dental Council register

PERFORMER_BDS_PLACE	Place of performer BDS qualification (from GDC / NHS Performers list)
PERFORMER_GENDER	
ADV_MAN_SERV	
ADV_MAN_SERV_COUNT1	YES "referral for advanced mandatory service"
ANTIBIOTICS	
ANTIBIOTICS_COUNT	
BEST_PRACTICE_COUNT	
CROWNS	
CROWNS_COUNT	
DECAYED_PERM	This is part of the DMFT index number of decayed teeth.
DECAYED_PERM_COUNT	This is part of the DMFT index if they completed the Decayed component. 0=N and 1=Y
ENDODONTIC_TREATMENT	
ENDODONTIC_TREATMENT_COUNT	
EXEMINATION_COUNT	
EXTRACT_ORTHO_COUNT	
FILLED_PERM	Number of filled permanent teeth (in DMFT component). This is part of the DMFT index
FILLED_PERM_COUNT	If the Filled component was completed or not. N=0, 1=Y. This is part of the DMFT index
FISSURE_SEALMENTS	
FISSURE_SEALMENTS_COUNT	
FLOURIDE_VARNISH_COUNT	
INLAYS	
INLAYS_COUNT	
MISSING_PERM	Number of missing permanent teeth . This is part of the DMFT index
MISSING_PERM_COUNT	if the M component was completed or not (0=N, 1 =Y). This is part of the DMFT index
RADIOGRAPHS	Number of radiographs taken (will only be from 2015 as not in legacy data)
RADIOGRAPHS_COUNT	If rads were taken or not (N=0, Y=1)
SCALE_POLISH_COUNT	
EXTRACTIONS_COUNT	If extractions were carried out

EXTRACTIONS	How many extractions
PERM_FILL_COUNT	If fillings were carried out. 0=NO, 1-Y
PERM_FILL	Number of permanent fillings and / or sealant restorations provided
RECALL_COUNT	Was a recall interval completed? Y=1, N=0
RECALL_INTERVAL	What is the recall interval? (3,6,12,18,24 months)
LAST_TREATMENT_DATE	This is date of last CoT
NUM_PERFORMERS	Total number of unique performers that the patient has seen over the 10 years. (Will be the same number in each row)
NUM_PRACTICES	Total number of different practice addresses the patient has attended over th 10 years.
DECAYED_deciduous	Decayed deciduous. This is part of the dmft index number of decayed teeth.
DECAYED_deciduous_COUNT	This is part of the dmt index f they completed the Decayed (deciduous) componenent. 0=N and 1=Y
FILLED_deciduous	Number of filled deciduous teeth (in dmft component). Double check this isn't fillings carried out. This is part of the DMFT index
FILLED_deciduous_COUNT	If the Filled (deciduous) component was complet dmfted or not. N=0, 1=Y. This is part of the DMFT index
MISSING_deciduous	Number of missing deciduous teeth . This is part of the dmft index
MISSING_deciduous_COUNT	if the M (deciduous) component was completed or not (0=N, 1 =Y). This is part of the dmft index
Sedation	Sedation
Treatment on referral	Treatment on referral
Further treatment within 2 months –	Further treatment within 2 months –

HES NHS digital CDS data

Link using DOB Name, URN NHS number	PANDA ID	dental GA (yes no)	Date of referral for DGA	Date of dental GA (if occurred)
-------------------------------------------	----------	--------------------	--------------------------	------------------------------------

Referral form data

Patient complaint	free text
-------------------	-----------

Reason for urgent care	free text
Indicate if following is requested (GA)	GA no GA
Previous dental history	free text
Main reason for referral	tick box
Teeth requested for treatment within referral	dental chart
Complexity score	tick box
Reason for referral	free text
Medical behaviour indicators	tick box
Patient anxiety question	5 questions on likert scale
radiograph included	yes no
Date of referral	date

Text message survey

	Text message Question	Potential response
1	Does your child have any pain in his/her mouth/teeth at the moment? Please reply: yes or no.	"Yes" / "No"
1a	If yes, how would he/she rate this pain from 1 (not too painful) to 10 (most painful pain ever)?	"1-10"
2	Has your child received any antibiotics for a dental problem recently for example, in the last year?	"Yes" / "No" / "Can't remember"
2a	If yes, do you remember how many days he/she was given and for how long did he/she take them? Just type your answer below.	Open text
3	In the last 3 months, has your child had any of the following problems: pain, difficult sleeping, problems eating/drinking?	"pain" / "sleeping" / "eating/drinking"
4	Overall, how was your experience of the service you attended for your child's dental treatment. Please reply: very good, good, neither good nor poor, poor, very poor?	"very good" / "good" / "neither" / "poor" / "very poor"
5	Did you feel the service your child attended for their dental treatment was appropriate for your child? Please reply: yes definitely, yes to some extent, no	"yes definitely" / "yes" / "no"
6	Would you recommend the service to family and friends? Please reply: yes, no, not sure	"Yes" / "No" / "Not sure"

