Primary: The primary outcome, measures whether a child has had a dental extraction under General Anaesthetic two years after referral as indicated in electronic patient records (recorded through HES data or through CDS patient records).

Secondary: The secondary outcomes to be considered in this project include:

- Waiting time until first appointment
- Number of sessions of treatment
- Whether a child was successfully seen and treated. For this outcome success is defined as treatment completed by a dentist that results in a child being referred back to their own dentist or discharged, pain free.
- The number of extractions and restorations as reported in NHS BSA data
- The courses of antibiotics taken during wait and treatment
- Participants referred back into the specialist pathway within two years of referral.
- Dental pain experienced by a child
- Participants views of their treatment and engagement with the dental profession (follow up of dental appointment) as indicated by the responses to the text message. Questions will include an adapted version of the NHS Friends and Family Test, questions on satisfaction, possible negative/adverse experiences, possible positive experiences, and an option for free text comments at the end of the survey.

Qualitative work will focus on two groups: (a) dental professionals (incl. triage, in-practice dental teams, CDS teams and referring practices) and (b) patients (incl. parents and children) accessing and using CFDPs.

(a) Dental teams' attitudes and beliefs regarding CFDP will be examined to better understand what worked well, what created barriers and look at how best to support implementation for such initiatives if they become routine practice.

In a qualitative approach, we will explore dental team beliefs, attitudes, and opinions regarding CFDPs and traditional pathways. To allow for the realist evaluation to take place, a combination of focus groups and one-to-one interviews will take place with the triage team and staff at CFDPs.

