A steering group, will monitor this study at periodic intervals. This group will include the Principal Investigator, University of Manchester staff, lay member of the community (Public and Patient Involvement (PPI) to ensure that the study is being conducted according to Good Clinical Practice Guidelines. An Oversight Committee (chaired by [name]) will monitor and feedback to both the research group and NIHR. Further PPI - patient and public involvement - will be sought for various aspects of the study including visits to practices for recruitment opportunities and through organisations which work with parents and children (such as sure start) to gain relevant opinions on the study, for example both the questionnaire and leaflet will be given to parents to fill in to test before the study begins.

The research will be monitored by the Lead Investigator on a weekly basis and at key project milestones.

The study will be subject to the audit and monitoring regime of the University of Manchester.

VIII. Data handling

The data controller will be the University of Manchester. Data will be collected through

- Clinical examinations. Dentists at the CFDP or CDS will fill out a Case report form (CRF) including information on treatment, antibiotic use (see Appendix B) - pseudo anonymised
- Text message surveys. Participants will answer text message survey at baseline, 1 year and 2 years after consent (See Appendix B). Surveys through text message survey (Text messages will be sent to participants using SafeMessage. SafeMessage is operated by FDS Consultants who are an NHS Business Partner (ODS: 8J025) who have met the following regulatory and legislative requirements: Fully completed NHS

DSPT, CyberEssentials Plus, Data stored in HSCN servers within ISO27001 certified, UK only data centres, DCB0219 met, Clinical Safety Officer, Data Protection Officer and Calidcott Guardian. The system is regularly penetration tested and complies with all the requirements of NHS Digital for the safe storage of sensitive data under GDPR.)

Answers from text message survey will be transferred to csv and pseudo anonymised

- Routinely collected data. Following participants consent, data will be linked and collected to be used within the study. This data will come from but not limited to NHS BSA, NHS England, HES, clinical records from the Community Dental Service, GDP and CFDP and referral forms (See appendix B) this data will be pseudo anonymised.

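### Survey item 3, the only pain item with a recall period and the only one on sleep and eating, is not tied to the mouth or teeth and so can count non-dental problems

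*Protocol*

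**What the plan says.** The secondary outcomes in the protocol (section VI, Outcomes) include "Dental pain experienced by a child". The same outcome is the fifth in the cost-consequences list (Cost effectiveness; section X, Data analyses). The research objectives name the source of the pain data: "Using a text message questionnaire, data will be collected from parents/guardians regarding antibiotic use, pain experienced and anxiety of the patient". Section VIII (Data handling) sets the timing: "Participants will answer text message survey at baseline, 1 year and 2 years after consent".

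The items are in Appendix B, Text message survey:

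- Item 1: "Does your child have any pain in his/her mouth/teeth at the moment". Its follow-up, item 1a: "If yes, how would he/she rate this pain from 1 (not too painful) to 10 (most painful pain ever".
- Item 2: "Has your child received any antibiotics for a dental problem recently for example, in the last year".
- Item 3: "In the last 3 months, has your child had any of the following problems: pain, difficult sleeping, problems eating/drinking". The listed replies are one word or phrase for each of the three symptoms.
- Items 4 and 5 ask about the service attended for the child's dental treatment.

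On analysis, section X says: "Analysis of secondary outcomes will be undertaken in a similar manner using covariate adjusted linear or logistic regression models as appropriate".

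**The concern.** The outcome is dental pain, but item 3 asks about pain, sleep and eating or drinking in general. Items 1, 2, 4 and 5 each carry a dental reference, so the gap in item 3 looks like an oversight. It matters because items 1 and 1a record only the moment of the text, which gives three points in time over two years. Item 3 is the only item that looks back over a period of pain, and the only one on functional impact.

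At stake is what the item 3 results can be said to show. Read as dental symptoms, they would overstate the level of dental problems in both pathways. The contrast between pathways could be weakened, or distorted if background illness or sleep trouble differs between the two groups of children. The replies carry no cause, so no analysis plan can repair this after collection.

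**Working it through.** **Wording, item by item**

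| Item | Subject | Dental reference | Period |
|---|---|---|---|
| 1, 1a | Pain and its severity | Yes | Current only |
| 2 | Antibiotics | Yes | About the last year |
| 3 | Pain, sleep, eating/drinking | No | Last 3 months |
| 4, 5 | Experience, suitability of service | Yes | None stated |

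Nothing elsewhere in the protocol limits item 3 to dental causes.

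**Is there a planned figure to reproduce?** Not for item 3. The only sample size in the protocol, 354 per group, is for general anaesthetic (GA) at 25% v 15%, two-sided 0.05, 90% power. It reproduces:

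- Uncorrected: n = [1.960 × √(2 × 0.20 × 0.80) + 1.2816 × √(0.1875 + 0.1275)]² / 0.10² = 334.2, rounded up to 335.
- With continuity correction: (334.2 / 4) × [1 + √(1 + 4 / (334.2 × 0.10))]² = 353.9, rounded up to 354.

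This confirms the GA calculation and says nothing about the survey.

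**Effect of non-dental background.** Take one symptom. Let p be the proportion with it from a dental cause and q the proportion with it from another cause, independent of the first. The observed proportion is p + (1 − p)q.

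*Equal q in both pathways.* The observed difference is (1 − q)(p₁ − p₂), whatever p₁ and p₂ are. For illustration, assume dental-cause rates of 25% and 15%. The protocol gives no symptom rates, and these values are no evidence about them.

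| Assumed q | Observed rates | Difference | Odds ratio |
|---|---|---|---|
| 0 | 25.0% v 15.0% | 10.0 points | 1.89 |
| 10% | 32.5% v 23.5% | 9.0 points | 1.57 |
| 20% | 40.0% v 32.0% | 8.0 points | 1.42 |
| 30% | 47.5% v 40.5% | 7.0 points | 1.33 |

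The level is overstated by (1 − p)q. In the 15% group that is 8.5 points at q = 10% and 25.5 points at q = 30%.

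*Unequal q, same assumed dental rates:*

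- q = 25% v 20%: (0.25 + 0.75 × 0.25) − (0.15 + 0.85 × 0.20) = 0.4375 − 0.3200 = 11.75 points, wider than the true 10.
- q = 20% v 25%: (0.25 + 0.75 × 0.20) − (0.15 + 0.85 × 0.25) = 0.4000 − 0.3625 = 3.75 points.
- No true difference, p = 20% in both, q = 25% v 20%: 0.80 × 0.05 = 4.0 points, all of it spurious.

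The wording therefore fixes neither the size nor the direction of the error.

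**The case against.** The strongest case on the other side has five parts.

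- **Dental pain has its own item.** Items 1 and 1a are specific to the mouth and teeth, and successful treatment is defined in part by the child being pain free. No text makes item 3 the dental pain outcome, and sleep and eating are not listed outcomes. All of this stands and limits the point to a supporting item.
- **Context guides the answer.** Item 3 follows two dental items, and the parents have consented to a dental study. Many will answer for teeth only. This stands and lowers the effective q, but by an unknown amount.
- **The questionnaire was to be tested with parents** (section VII). That does not change the wording, which still lacks a dental reference in V1.4, dated 02/04/2024, although texting was scheduled from May 2023.
- **Dilution is not assured.** This is correct. A reader might infer that the pathway difference is necessarily diluted. That needs equal background in both pathways, which a non-randomised comparison does not secure.
- **A loss of power cannot be calculated.** A reader might apply 354 per group and 25% v 15% to item 3 and quote one. The protocol does not support this. Those figures belong to the GA outcome. Recruitment in the Child Friendly Dental Practice (CFDP) group was low and is being supplemented with unconsented referral records, while the survey follows consent. The number of CFDP families who can be surveyed is therefore not 354.

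**Conclusion.** The point holds as a defect of specificity in one survey item. Item 3 can count non-dental problems, and its replies cannot be sorted by cause afterwards. If the background is equal in both pathways and independent of dental problems, the risk difference shrinks by the factor (1 − q). If it differs, the bias can go either way. The protocol gives neither q nor any rate for item 3, so the figures above are illustrations and no power statement is warranted.

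The dental pain outcome is not lost, since items 1 and 1a still measure current dental pain, and the primary GA outcome is untouched. What is affected is three-month pain and the impact on sleep and eating or drinking. This is a worthwhile, inexpensive improvement in validity and not a threat to the study's main conclusion.

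**What to change.** For the remaining waves, reword item 3. Replace the first use of the word *problems* with *because of his/her mouth or teeth*, and correct *difficult* to *difficulty* before *sleeping*. Keep the three-month period and the three symptoms.

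For handling the replies:

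- Flag every reply by wording version and compare pathways within the same wording.
- Do not pool replies to the two wordings.
- Do not read a change from a current-wording baseline to a reworded follow-up as a real change.
- Report replies to the current wording as symptoms of any cause. Where only that wording exists, base the dental pain outcome on items 1 and 1a.

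The cost is one changed text message and a minor amendment. The timetable in section VI places survey rounds in May to July 2024 and May to August 2025, both after the date of this version, so later replies can still benefit. The real downside is that early replies will not be comparable with later ones. Wording will also be partly confounded with survey wave, so adjusting for a wording indicator would not cleanly separate the two. This is why the comparison should stay within one wording.
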